3.2.3 Mediators, Moderators, Confounders, & Implementation Measures

Mediators, moderators, confounders, and implementation measures will be assessed at the parent, provider and practice levels. The interventions are likely to influence mediators at the practice level (EMR documentation and practice readiness, climate, attitude) and at the provider level (oral health knowledge and self-efficacy). Subsequently, providers improved oral health knowledge and communication of oral health facts to parent is likely to influence parent-level mediators (illness perception and parent self-efficacy to take the child to the dentist). The moderators for the relationship between the interventions and the primary/secondary outcomes are parental socio-demographics, health literacy and social support and the confounders are child medical illness. Provider socio-demographics can also be a moderator to this relationship. See Sections 4 (Figure 4.2.1) for more details on mediators, moderators and confounders and Table 8.1.1 for implementation measures and for more details regarding how these measures will influence the primary and secondary outcomes.

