5.2 Subject Exclusion Criteria

An individual who meets any of the following criteria will be excluded from participation in this study:

Child:

- Presence of any serious medical or behavioral condition (e.g. cerebral palsy, autism) that precludes participation in the dental screening

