All parents of 3-6 year-old Medicaid-enrolled children attending a WCV in the selected practices during the recruitment period will be invited to participate in the study. Based on the data from the 18 practices, we expect 7,421 Medicaid-enrolled children aged 3-6 years to have a WCV at the pediatric offices per year. In our pilot study, the participation rate was 95%, hence similar strategies will be implemented in the main trial.

A team consisting of a research assistant and dental hygienist will be assigned to one practice at a time to be on-site daily for recruitment of caregiver-child dyads at larger practices. A floating team will recruit at multiple smaller practices simultaneously. The available sample pool for the 3-month recruitment period is 1,855 (25% of 7,421). We anticipate that 5% will be ineligible based on inclusion and exclusion criteria, thus reducing the potential sample to 1,762 (95% of 1,855). Based on our experiences recruiting and enrolling parent/caregivers in 2 pilot practices,

we expect a participation rate of 95% (of 1,762), giving us an available potential sample size of 1,674 per 6 practices enrolled. For the total of 18 practices, we can expect a potential sample size of 5,022 from whom we can recruit the target sample size of 1024 participants (512 per arm for 2 arms) required to test the hypothesis of the study. Therefore, our goal of recruiting 56 to 57 participants per practice given the potentially large population pool of each practice is an achievable approach to meet the main trial sample size. The recruitment is expected to be completed within a 9-month time frame.

The recruitment and enrollment strategies proved to be effective in the pilot study will be used for the main trial as follows:

- When making appointment reminder calls, practice staff will give a brief overview of the study (using a recruitment script) and ask caregivers to come early to fill out the consent forms and questionnaires.
- Tailored to the practice's or provider's preference, the medical assistant may approach caregivers first, before study staff explain and obtain consent. An alternative approach is that study staff will approach caregivers in the waiting room.
- All 3 questionnaires, i.e. Illness Perception Questionnaire-Revised for Dental (IPQ-RD), Parent Questionnaire, and Parent Exit Questionnaire, can be completed on paper or tablet according to the caregiver's preference.

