8 STUDY PROCEDURES / EVALUATIONS

8.1 Study Procedures/Evaluations

The following is a summary of the study procedures and evaluations. Study procedures include interventions, and procedures performed to assess the primary outcome, secondary outcomes, mediators, moderators and confounders. Measures or interventions will occur at the socioecological levels of child, parent/caregiver, provider, and practice. There will also be implementation evaluation at each of these levels except the parent/caregiver. See Table 8.1.1 for more details on the measures, sources, and timeline. According to the timeline of study procedures and evaluations, WCV #1: Baseline Visit = T_0 ; WCV #2: Follow-up Visit = T_3 ; and WCV #3: Final Study Visit = T_6 .

Table 8.1.1 Summary of measures, sources, and timeline

Socioecological levels	Implementation Evaluation	Measures	Score	Source	Timeline
Child	Reach # recruited % attrition Participant characteristics (socio-demographics)	Effectiveness Primary outcome: Dental attendance Secondary outcomes: New caries Oral hygiene Frequency of sweet food & drinks OH-related quality of life Cost	% frequency # of decayed, filled teeth (dft) % freq. tooth brushing % freq. sweet food & drinks ECOHIS overall score Direct dental costs Non-dental direct & dental indirect costs	ICDAS (Pitts, 2004); Medicaid claims ICDAS (Pitts, 2004) NHANES III (CDC) Food Frequency Qx, NHANES 2003-2004 (Dye et al., 2010); YRBS 2017(CDC, 2017) Pahel et al., 2007) Medicaid claims Annotated Cost Qx (Thompson & Wordsworth, 2001)	T ₀ , T ₁ , T ₃ , T ₄ , T ₆ , T ₇ T ₀ , T ₃ , T ₆ T ₀ , T ₃ T ₁ , T ₄ , T ₇
	Confounder: Child medical illness	Overall score	Chi & Rakllos, 2012		T ₀ , T ₃ , T ₆
Parent/ caregiver		Mediators: IPQ-RD Moderators: Socio-demographics Health literacy Social support	Overall & mean construct scores Overall score % categories % mean scores	[name], 2016 (Detroit Dental Health Project, 2004) NHANES III (CDC) Morris et al., 2006 Zimet et al., 1988	T ₀ , T ₁ , T ₃ , T ₄ , T ₆
Provider	Implementation/ Fidelity Observation/ audiotape Parent Exit Qx Adoption & Maintenance % prescriptions + list of dentists given	Mediators: OH knowledge Self-efficacy Confounder: Socio-demographics	% mean scores % categories	Open Wide (NMCOHRC) PACT (AAP) (Lewis et al., 2009)(Quinonez et al., 2014) NHANES III (CDC)	T ₋₁ , T ₂ T ₋₁

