8.1.1 Child-level

The primary (i.e. dental attendance) and secondary outcomes (i.e. new decay, oral hygiene, frequency of sweet food and drinks, oral health-related quality of life, and dental-related costs) are also implementation measures of effectiveness. Child medical illness is a confounder.

Child dental attendance (i.e. receipt of dental care) will be assessed through:

- Clinical dental screenings will be performed at all 3 WCVs (T_0 , T_3 , and T_6) by a trained and calibrated dental hygienist according to the International Caries Detection and Assessment System (ICDAS). The screenings will be used to identify a change in oral health status between WCVs #1 and #2 (T_0 and T_3) and WCVs #2 and #3 (T_3 and T_6) which is defined as a restoration (ICDAS ≥ 3) or extraction of ≥ 1 tooth previously identified with an active ICDAS lesion code ≥ 3 at T_0 or T_3 that would not be exfoliated naturally based on child's age. See ICDAS Assessment form (Appendix E). More details on the screening and decision algorithm will be outlined in the MOP Section 5.
- B2: Dental Attendance & Cost Questionnaire: Study staff will contact caregivers 6 months after WCVs #1 and #2 (T_1 and T_4) to ask whether their child had a dental visit or if they made a dental appointment for their child since the previous WCV (Appendix E).
- Medicaid claims files: Data will be abstracted by study staff to verify child's receipt of dental care after each WCV (T_1 , T_4 , and T_7) and entered on the Medicaid Claims Abstraction form. Current Dental Terminology (CDT) codes used for billing will be used to determine if the child received preventive or restorative procedures in the past 12 months. Dental emergency department (ED) visits will be identified by linking diagnosis codes (Appendix E) to ED claims using the International Classification of Diseases, Tenth Revision, Clinical Modification (ICD-10-CM). See Medicaid Claims Abstraction form (Appendix E) for preventive and restorative CDT codes and ICD-10-CM codes.
- COVID-19 Questionnaire: At WCV3, actively enrolled parent/caregivers will complete a short (7 item) COVID-19 Questionnaire which asks if they have altered their behavior related to taking their child to the dentist due to the COVID-19 pandemic.

Secondary outcomes and child medical illness (i.e. confounder) will be assessed as follows:

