will be modified by using a linear model (identify link) for GEE, modeling the mean response over time as a summary measure. These outcomes will each be tested for normality using the Shapiro-Wilk statistic; outcomes for which normality is violated will be transformed where appropriate or an alternative model used. For count outcomes (e.g., dft accumulated over time), we will use a loglinear model (log link) assuming a negative binomial or other appropriate (e.g., zero-inflated negative binomial) distribution. For proportion outcomes (e.g., dt/dft), we will use GEE with a logit link, assuming the proportion follows a beta binomial or zero-inflated beta binomial distribution (Albert et al 2014). Similarly, we will fit appropriate GEE models to test for the effect of each implementation strategy on the corresponding outcome (e.g., % prescriptions given as a measure of adoption). As in the dental attendance analysis, the intervention indicator as well as pertinent baseline variables will be included in the model. In addition, interaction terms (baseline variables by intervention) will be included to test for possible effect modification.

For secondary analyses, a GLIMMIX model approach will be considered as an alternative, which may more easily allow for more than one cluster level if needed. Another alternative approach is to model the repeated measurements (again using GEE or GLIMMIX) which will add an additional cluster level – namely, for individuals). Goodness of fit of alternative models will be compared using QIC for GEE (or AIC for GLIMMIX).

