help reveal the importance of each of the multiple components of the bundled intervention. For example, we can estimate the proportion of intervention effect mediated by 'compliance' with regard to EMR documentation. A relatively high mediation proportion will suggest efficacy of the corresponding component.

We have previously developed a generalized causal mediation (GCM) analysis methodology and an accompanying R package (Albert & [name], 2011; Albert, Unpublished; Cho & Albert, Unpublished) which we will use to estimate and test each path effect and its proportion of the total intervention effect. The GCM method allows mediators and final outcomes of different types, including continuous, binary, and count (assumed to have normal, Bernoulli, and Poisson or negative binomial distributions, respectively). These options will accommodate the mediators and final outcome (dental attendance, summarized as a binary response) in our model. Each outcome (including mediators) is modeled using a generalized linear model that includes as covariates possible baseline confounders as well as causally preceding variables according to the causal model (as in Figure 4.2.1). The method uses an extended version of the mediation formula and assumes an extended version of the sequential ignorability assumption. (Albert et al., Unpublished) Bootstrap resampling is used to compute confidence intervals and a cluster bootstrap option is available to account for unexplained between-cluster (e.g. provider) variability.

Adjustment for Baseline Characteristics: Estimated intervention effects will be adjusted for the following baseline socio-demographic variables: child's age, race, and caregiver SES, education, and marital status.

Model Assumptions: We will assume that the probabilities of dental care receipt follow a logistic regression model with the included covariates and random effects. Per the standard approach, random effects will be assumed to be independent, normally distributed, and outcomes assumed conditionally independent given the random effects. If multiple random effects (e.g., for different cluster levels) are used, they will be assumed to be independent. For secondary outcomes, analogous assumptions, including the assumption of the correct link function, will be made.

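### Section 12.4 should name prior-year dental attendance, T0 medical illness and the T0 secondary-outcome values as covariates; leaving them unnamed costs precision with 9 v 9 practices

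*Combined protocol and SAP*

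**What the plan says.** Enrolment does not depend on past dental care. Section 5.3 states: "All parents of 3-6 year-old Medicaid-enrolled children attending a WCV in the selected practices during the recruitment period will be invited". The only child-level exclusion, in Section 5.2, is "Presence of any serious medical or behavioral condition (e.g. cerebral palsy, autism) that precludes participation in the dental screening". Section 5.4.1 restricts the randomisation on three practice features (Medicaid share in two bands, patients per provider, and Cuyahoga versus other counties). Attendance is not one of them.

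Section 12.4 describes the covariates in three places:

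- **Primary analysis:** a proportional odds GEE clustered on practice, with a small-sample standard error correction. Covariates are the intervention indicator and an unlisted group of baseline variables regarded as possible confounders.
- **Secondary outcomes:** the indicator plus relevant baseline variables, again unlisted. Binary and ordinal outcomes get a summary over time. For continuous outcomes the plan describes "modeling the mean response over time as a summary measure".
- **Adjustment for Baseline Characteristics:** "Estimated intervention effects will be adjusted for the following baseline socio-demographic variables", namely "child's age, race, and caregiver SES, education, and marital status".

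On child medical illness, Section 3.2.3 says "the confounders are child medical illness", and Section 8.1.1 has it abstracted from the EMR at T0, T3 and T6. Table 8.1.1 lists "Primary outcome: Dental attendance" with a timeline that appears to start at T0, although the row is broken in the available text. Section 8.1.1 says claims codes are "used to determine if the child received preventive or restorative procedures in the past 12 months", with abstraction after each WCV (T1, T4, T7).

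**The concern.** Whether a child went to the dentist last year is the obvious predictor of whether the child goes next year. The plan relies on that link itself: its control rate of 0.30 is the pilot's past-year attendance rate. Children who already attend can score 2 on the primary outcome with no help from the intervention. Attendance may well differ between practices, whose Medicaid share runs from 22% to 86% in Table 4.1.1.

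The one list the plan gives leaves this predictor out, along with the confounder the protocol names. The other two statements are open. Section 12.4 also plans preliminary tests of baseline differences between groups. It does not say these will select covariates, but an unlisted set leaves room for choices made after arm-level data are seen.

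Brushing, diet and ECOHIS are collected at T0, T3 and T6. Section 12.4 neither names the T0 value as a covariate nor says that it stays out of the summary over time.

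**Working it through.** **Inputs from Section 12.2:** 512 per arm, 25% dropout, 9 practices per arm, ICC 0.04, rates 0.46 and 0.30, pooled z test at two-sided 0.05, stated power 80%. **Assumptions, because the documents give no figure:** a baseline attendance rate of 30% (the pilot's past-year rate), a baseline ICC of 0.04 (the outcome ICC), and a baseline-to-follow-up correlation r.

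**1. The plan's own figure.** Analysed per arm: 512 × 0.75 = 384, or 384/9 = 42.67 per practice. Design effect = 1 + 41.67 × 0.04 = 2.667. Effective n = 384/2.667 = 144.0 per arm. Null SE = √(2 × 0.38 × 0.62/144) = 0.0572; alternative SE = √((0.46 × 0.54 + 0.30 × 0.70)/144) = 0.0564. Power = Φ((0.16 − 1.96 × 0.0572)/0.0564) = Φ(0.85) = 80.2%. The stated 80% reproduces.

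**2. Chance baseline gap between arms.** With 512 enrolled per arm (56.9 per practice), the design effect is 1 + 55.9 × 0.04 = 3.236 and effective n is 158.2. SD = √(2 × 0.30 × 0.70/158.2) = 0.0515, about 5 points. A gap above 5 points has probability 33%, and above 10 points 5%. With a baseline ICC of 0.02 the SD is 4.2 points; with 0.01 it is 3.6. These figures ignore the restricted randomisation.

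**3. Shift in one trial.** If the baseline and follow-up arm differences have similar SDs, a gap of d points moves the unadjusted estimate by about r × d. For r = 0.2 to 0.5, a 5-point gap moves it 1.0 to 2.5 points and a 10-point gap 2 to 5 points, against a planned effect of 16.

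**4. Power with the baseline value as covariate.** The variance is multiplied by (1 − r²), so effective n becomes 144/(1 − r²).

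| assumed r | variance ratio | nominal power |
|---|---|---|
| none | 1.00 | 80.2% |
| 0.2 | 0.96 | 81.8% |
| 0.3 | 0.91 | 83.8% |
| 0.4 | 0.84 | 86.6% |
| 0.5 | 0.75 | 90.1% |

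**5. Simulation check.** A 9 v 9 trial with 43 children per practice, rate 0.30 and ICC 0.04 was simulated under three sets of assumed correlations (practice level 0.5 to 0.8, child level 0.3 to 0.6 on a latent scale). These gave correlations between the baseline and follow-up arm differences of 0.38, 0.55 and 0.65. A practice-level t test was compared with ANCOVA on the practice baseline rate, as a stand-in for the GEE.

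- No true effect: the mean estimate is about 0. Type I error is 4.7-5.3% unadjusted and 5.0-5.4% adjusted.
- Among the roughly 15% of null trials with a baseline gap above 8 points: 10-18% unadjusted, 5-6% adjusted.
- True 16-point effect: power is about 77% unadjusted, and 82%, 88% and 93% adjusted. The unadjusted value is below 80% because the practice-level test uses t with 16 degrees of freedom.

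**6. T0 inside a three-visit mean.** The expected arm difference at T0 is zero. If the effect is δ at T3 and at T6, the mean over T0, T3 and T6 shows (0 + δ + δ)/3 = 2δ/3.

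**The case against.** A reader might infer that chance baseline differences will be reported as intervention effect, which would be bias. The documents do not support that. Practices are randomised, the GEE clusters on practice, and a small-sample correction is planned, so chance differences between practices are already in the standard error. The simulation agrees.

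A reader might also infer that prior attendance is excluded from the model. It is not: the list covers socio-demographic variables, and the open wording elsewhere in 12.4 could admit attendance and medical illness. That stands, and it makes the fault one of pre-specification: the reader cannot tell which covariates the model will contain.

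Other limits also stand:

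- New dft is defined against earlier screenings (Sections 3.2.2 and 8.1.1), so T0 status already enters the caries outcome.
- A full pre-baseline year of claims is not already in hand. Abstraction is scheduled only after each WCV, first at T1, to verify care received after that visit.
- Restricting on Medicaid share and county may remove some between-practice variation in attendance. If it removed half (an assumption), the SD would be √(0.42 × (0.02 + 0.96/56.9)/9), about 4.1 points.
- The power formula is for a difference in proportions, while the primary model is proportional odds, so the gains carry over only approximately.
- The mean over time applies to continuous outcomes such as ECOHIS; brushing and diet get ordinal summaries. The text does not say T0 enters either, and the primary score counts follow-up years only.

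**Conclusion.** The point holds as a matter of precision and pre-specification. The only named adjustment set omits prior-year attendance, T0 medical illness and the T0 values of brushing, diet and ECOHIS, and the rest of 12.4 does not settle whether they are included.

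The estimate is unbiased on average and overall type I error stays near 5%, provided recruitment within practices does not differ by arm. The loss is power and protection in an unlucky allocation. The chance baseline gap has an SD of about 5 points under the stated assumptions, and about 3.6 to 4.2 with a smaller baseline ICC. Nominal power rises from 80% to about 82-90% for r between 0.2 and 0.5. That range is assumed; the documents give no value.

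The loss of one third of the effect on a continuous secondary outcome arises only if T0 is averaged in, which the text leaves open.

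**What to change.** In 12.4:

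1. Name two further covariates in the primary model: any Medicaid dental claim in the 12 months before WCV #1, with a separate category for incomplete prior enrolment, and T0 child medical illness. Fix the coding of medical illness in advance. Table 8.1.1 gives an overall score and Section 8.1.1 ten groups; with 18 practices, fewer parameters are safer.
2. Make the primary, secondary and Adjustment paragraphs refer to one closed covariate list.
3. For brushing, diet and ECOHIS, state that the summary uses T3 and T6 only, with the T0 value as covariate.

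The cost is SAP wording and a claims extract reaching back 12 months before WCV #1. Some children will have incomplete prior enrolment, and the added category deals with them. No new visit or questionnaire is needed.

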13 SOURCE DOCUMENTS AND ACCESS TO SOURCE DATA/DOCUMENTS

Study staff will maintain appropriate research records for this study, in compliance with ICH E6, Section 4.9 and regulatory and institutional requirements for the protection of confidentiality of subjects. CWRU will permit authorized representatives of NIDCR, the CC at UCSF and regulatory agencies to examine (and when required by applicable law, to copy) research records for the purposes of quality assurance reviews, audits, and evaluation of the study safety, progress, and data validity.

All records with identifiable information will be kept in secured locked storage units or stored in secure online databases. Only local (i.e. study staff) at CWRU, the Medical Monitor/DSMB, and NIDCR staff appointed to the trial will have access to the records. Access by the DSMB and NIDCR staff is for the purposes of quality assurance reviews, audits, and evaluation of the study safety and progress.

Specific original documents and data records include, but are not limited to:

- **Parent Consent chart** contains all participant-identifying information. The chart includes the signed consent form, Consent Documentation form, the Parent Contact Info form, Unanticipated Problem or Serious Adverse Event forms, Telephone Contact log and Parent Reimbursement form. These documents will contain the participant's name and other confidential information (i.e. names of child/children and other family members). (Electronic and Paper Based)
- **Parent/Child Research chart** includes Case Report Forms (CRFs) and the Progress Notes Checklist. Examples are: child's ICDAS caries dental assessment form (WCVs #1, #2, & #3); and parent/caregiver's IPQ-RD and Parent Questionnaire (WCVs #1, #2 & #3) along with follow-up questionnaires (WCVs #1 & #2). (Electronic and Paper Based). Medical abstraction for child illnesses will be from the EMR of the participating practices. Medicaid dental claims data will be used to assess dental attendance for the child.
- **Provider Consent chart** contains all participant-identifying information for providers. The chart includes the signed consent form, consent documentation form, and provider sociodemographic questionnaire. (Electronic and Paper Based).
- **Provider Research chart** will include the provider training pre- and post-tests, and data from the provider score card from the study staff observations. (Electronic and Paper Based). Structured interview transcripts will also be stored in the provider research chart.
- **Tracking logs (in RedCap)** (Electronic)
- **Electronic Audio Recording** of patient encounter to evaluate implementation of delivery of oral health facts. Recordings of structured interviews will be kept until the interview has been transcribed.
- **Memoranda** (paper-based)

Some case report forms and all abstractions from EMR and Medicaid dental claims will be completed by study staff (Research Assistants, the Research Associate, or Project Coordinator, depending on the event). Exceptions will be the questionnaires (IPQ-RD and Caregiver

Questionnaires), Parent Contact information and Consent form(s) that will be completed by the parent/caregiver. The study staff will complete all provider audit forms. Completion of essential documents will follow the guidelines outlined in Section 10.4 of the MOP for Case Report forms. Data will be handled in accordance with GCP, U.S. federal regulations, local regulations (if applicable), and instructions from NIH. All essential documents should be filled out completely and signed by the study staff collecting or recording the data. When necessary, essential documents (like consent/assent forms) will be reviewed, signed and dated by the principal investigators or study staff designated by the principal investigators.

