5.4.2 Masking Procedures

Parent/caregiver participants will be blinded to the intervention arms of the main trial. Furthermore, parent/caregiver participants will not be aware of what is involved in the study procedures being followed at other clinics. Study staff conducting dental screenings will also be blinded.

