6.3.2 Procedures for Monitoring Intervention Fidelity

Arm A

Providers' implementation of the provider-level intervention will be assessed at all 3 WCVs. Two - three of each provider's OH encounters with parent/caregiver will be observed or audiotaped and then evaluated by the study staff using a standardized communication skills checklist (Appendix E) at WCV #1 and WCV#2. The results of the observation/audiotaping will be given to the provider as a scorecard to provide feedback regarding whether the provider met the established target goals which are elaborated in detail in the Fidelity Monitoring Plan (Appendix B). All enrolled caregivers will complete an exit questionnaire (Appendix E) after the OH encounter to assess whether the provider communicated the OH facts and gave them the prescription and list of dentists. So, *Provider-level fidelity measures* to assess whether providers communicated the core OH facts to caregivers and delivered the prescription to go to the dentist and list of area Medicaid-accepting dentists include: 1) standardized communication skills checklist completed by study staff and 2) parent exit questionnaire (Appendix E).

Providers' implementation of the practice-level intervention will be assessed at all 3 WCVs. Study staff will complete monthly EMR audits (at all 3 WCVs) of all enrolled patients' EMR chart to assess whether providers' OH documentation was complete.

The *practice-level fidelity measure* to assess adoption of the intervention is the EMR Audit of Practice form completed by study staff (Appendix E).

Arm B

Since Arm B does not receive the interventions, monitoring procedures outlined below will be used to monitor baseline rate and check for contaminations between study arms.

Two - three of each provider's OH encounters will be randomly selected for observation/audiotaping and evaluation by study staff using the same standardized communication skills checklist used in Arm A. Scorecards will not be given to Arm B providers, but evaluation with the checklist will serve to document the communication of OH facts due to enhanced usual care.

Study staff will complete monthly EMR audits using the EMR Audits of Practice form (at all 3 WCVs) for 20% of enrolled patients' EMR chart to assess whether any oral health documentation was completed despite not receiving EMR training. (Appendix E).

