7.2 Parent/Caregiver and Child

7.2.1 Baseline Visit: WCV #1

At WCV #1 (T₀: Day 0)

Before Provider Encounter

- Study Staff will recruit 1024 parent/caregivers and their children from the 18 practices (approximately 56-57 participants/practice) using an in-person approach. Parents/caregivers attending well-child visits with 3-6 year old children will be approached for participation.

- In the waiting area/exam room of the pediatric practice, study staff will review inclusion/exclusion criteria as outlined on the screening survey to determine parent/caregiver and child eligibility (Refer to Sections 5.1, 5.2).
- Review the written consent form with the potential participant; study staff signs the consent form acknowledging that informed consent was reviewed and caregiver signs acknowledging consent was obtained (Appendix C: Consent forms).
- In the waiting area/exam room of the pediatric practice, study staff will obtain contact information.
- In the exam room, caregivers will complete the following self-administered Baseline questionnaires: A1: Illness Perception Questionnaire-Revised for Dental (IPQ-RD) and A2: Parent Questionnaire (Appendix E: Questionnaires & forms).
- In the exam room, dental hygienist will perform child dental screening examination and study staff will record results of the dental screening examination. Results will not be available to the provider, unless the hygienist finds that the child has urgent needs that require immediate attention. (Appendix E: Questionnaires & forms).

During Provider Encounter in the Exam Room

- Caregivers attending WCV's will receive OH information, prescription to take the child to the dentist + list of local Medicaid-accepting dentists from provider, based on study arm.
- Caregivers attending WCV's may have study staff audiotape or directly observe the provider encounter to evaluate provider's delivery of OH communication (for a sample of visits).

After Provider Encounter in the Exam Room/Waiting Area

- Caregivers will provide feedback about the OH information given to them during the medical visit with a short self-administered exit questionnaire (A3: [Appendix E: Questionnaires & forms]).
- Caregivers will be given the B1: Follow-up IPQ-RD (Appendix E: Questionnaires & forms) to be completed and returned (in postage paid envelope or in person, based on participant preference).

After WCV #1 (T₁)

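### Medicaid claims, the first-ranked source of the primary outcome, are abstracted manually by staff who are not listed as masked and who can learn the practice's arm

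*Combined protocol and SAP*

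**What the plan says.** Section 3.2.1 scores attendance from a hierarchy: Medicaid claims first, then change seen at the dental screenings. Section 8.1.1 describes the claims step: "Data will be abstracted by study staff to verify child's receipt of dental care after each WCV", with the result entered on an abstraction form. Section 13 adds that "all abstractions from EMR and Medicaid dental claims will be completed by study staff (Research Assistants, the Research Associate, or Project Coordinator", the role varying with the event.

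Section 5.4.2 names two masked groups. For caregivers: "Parent/caregiver participants will be blinded to the intervention arms of the main trial". For examiners: "Study staff conducting dental screenings will also be blinded". It names no other role.

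Sections 6.3.2, 6.4, 14.2.1 and 14.2.2 give study staff several tasks that show the arm. They observe or score recorded encounters, audit all enrolled charts in Arm A but 20% in Arm B, and give feedback in one arm only ("Scorecards will not be given to Arm B providers"). Research Assistants also check completed questionnaires.

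For screening, section 7.2.1 has the hygienist examine while "study staff will record results of the dental screening examination". Section 5.3 describes the team used at larger practices: "A team consisting of a research assistant and dental hygienist will be assigned to one practice at a time to be on-site daily".

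**The concern.** The first source of the primary outcome passes through a person who can know the allocation. If that person searches harder, or settles doubtful dates or codes differently, in one arm, the attendance rates differ for a reason unrelated to the intervention. The error could run either way: towards a false positive, or towards hiding a real effect. The planned intention-to-treat analysis would not detect or correct it, and the missing-data sensitivity analysis in section 12.4 does not address it, because a missed claim looks like non-attendance and not like a missing value.

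Claims data are usually credited as an objective outcome source. Here that credit depends on an abstraction step whose masking the plan does not state.

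**Working it through.** **1. Can the permitted abstractors learn the arm?**

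- Section 13 allows Research Assistants, the Research Associate or the Project Coordinator. It does not fix which of them handles claims.
- Section 14.2.2 has Research Assistants check completed questionnaires. The exit form asks whether the provider gave a prescription and a list of dentists (sections 6.3.2 and 6.4). Section 4 says Arm B gives neither. Reading these forms therefore shows the arm.
- Encounter observation, chart audits and Arm A scorecards go to study staff, with no role excluded.
- Allocation is by practice, so learning it for one child reveals it for all children at that practice.

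No section states that an abstractor must be someone without this exposure.

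**2. Is there room for effort or judgement?** Section 8.1.1 requires staff to abstract the claims files, match procedure codes to the preventive and restorative lists, decide whether they fall in a 12-month period, and link diagnosis codes to emergency-department claims. Section 7.2.5 allows visits well outside the window, so the period to which a claim belongs is not always obvious. The two-person check in section 14.2.2 covers entry and verification of paper forms. It is not a second abstraction.

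**3. The plan's own figures.** Section 12.2 assumes 0.46 against 0.30, ICC 0.04, 25% dropout, 9 practices and 512 children per arm.

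- Analysed per arm: 512 × 0.75 = 384, or 384/9 = 42.67 per practice.
- Design effect: 1 + (42.67 − 1) × 0.04 = 2.667.
- Effective n per arm: 384/2.667 = 144.
- Power of the two-sided 0.05 pooled z test: 0.802. The stated 80% reproduces and is not in question.

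**4. Illustration of size.** The capture rates below are assumptions; the documents give none. Suppose no true effect, true attendance π in both arms, all attenders found in Arm A and a share s found in Arm B.

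- Spurious difference: d = π(1 − s).
- Rejection rate: 1 − Φ[(1.96·SE₀ − d)/SE₁] + Φ[(−1.96·SE₀ − d)/SE₁], with SE₀ pooled and SE₁ unpooled, n = 144.
- Worked case, π = 0.30 and s = 0.90: rates 0.30 and 0.27, d = 0.03, SE₀ = √(2 × 0.285 × 0.715/144) = 0.0532, SE₁ = √((0.2100 + 0.1971)/144) = 0.0532. The rejection rate is 8.7%.

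| π | s | Spurious difference (points) | Rejection rate |
|---|---|---|---|
| 0.30 | 0.98 | 0.6 | 5.1% |
| 0.30 | 0.95 | 1.5 | 5.9% |
| 0.30 | 0.90 | 3.0 | 8.7% |
| 0.46 | 0.98 | 0.9 | 5.3% |
| 0.46 | 0.95 | 2.3 | 6.8% |
| 0.46 | 0.90 | 4.6 | 12.3% |

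The planned difference is 16 points, so these biases are 0.6/16 = 4% to 4.6/16 = 29% of it. The calculation uses the planning z test, not the proportional-odds GEE of section 12.4.

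**5. Screening.** Section 5.4.2 asserts blinding of screening staff. Sections 7.2.1 to 7.2.3 place the screening before the provider encounter, and section 14.2.1 withholds baseline results at follow-up. The first does not shield staff from what other families at the practice have already received by the second and third visits. The second hides earlier findings, not allocation. No procedure is stated for keeping staff masked to arm at a site where every child is in the same arm.

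**The case against.** The strongest reply is that claims are created by dental billing outside the trial and read against a listed code set. A code is there or it is not, so knowing the arm has little to act on. Most of this stands. It limits the likely size and makes the larger losses in the table hard to reach, but it does not cover the search, dating and linkage steps.

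A reader might infer that on-site field staff abstract the claims. The text does not support that: two of the three permitted roles are not described as on-site recruiters, and the role is left open.

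A reader might also infer that the hygienist cannot be blind, being on site daily beside a research assistant. The documents do not show this. No section gives hygienists a task that reveals the arm, screening comes before the encounter, earlier results are withheld, examiners are calibrated, and the wording in 5.4.2 can be read to include the recorder. The decision algorithm sits in Manual of Procedures section 5, which may say more. What remains is a missing description of how blinding is kept.

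The screening fallback also has limited reach. It can change the score only for children with an earlier lesion and no claim. With the pilot's 36% untreated caries (section 2.2), attendance of 30% to 46% and assumed independence, that is 0.36 × 0.54 = 19% to 0.36 × 0.70 = 25% of children.

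**Conclusion.** The point holds for claims abstraction. The plan relies on manual abstraction of its first-ranked primary source, lists none of the permitted abstractors as masked, gives staff in those roles ways to learn the arm, and describes no masked or duplicate abstraction. That staff will know the arm is a well-founded inference; the documents do not say so outright.

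The size is unknown. The figures above rest on assumed capture rates and on the plan's ICC and dropout. They should not be read as an estimate of the trial's false-positive rate. With billing codes, the lower end is more plausible. This is a reason for a cheap improvement, not a reason to distrust the primary comparison.

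The screening point is secondary: blinding is stated without a means of keeping it. It is not a contradiction, and the documents do not support saying that the workflow cannot deliver blinding.

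**What to change.** 1. Change sections 8.1.1 and 13 so that claims are linked by study ID, stripped of practice, provider and arm, and flagged by program from the CDT and ICD-10-CM lists already on the abstraction form. Make any manual decision on that masked file.
2. Add claims abstraction to the masked steps in section 5.4.2.
3. Where existing staffing allows, the person who records screening results should not do encounter scoring, exit forms or EMR audits for the same practice. Where it does not, the report should say that masking of screening staff could not be assured.

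Items 1 and 2 cost a little data-management programming and can be done before database lock, even if visits are complete. Item 3 may be hard in a two-person team, which is why it is conditional. No change to how hygienists are scheduled across practices is needed.
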